Comparison of Lidocaine versus Bupivacaine Spinal Anesthesia in Total Hip Arthroplasty: A Randomized, Double-Blind, Prospective Study

NCT02818894

Date: April 26, 2017

IRB00083867

Comparison of Lidocaine versus Bupivacaine Spinal Anesthesia in Total Hip
Arthroplasty: A Randomized, Double-Blind, Prospective Study

Investigators:

[REDACTED]

[REDACTED]

ABSTRACT

Spinal anesthesia is commonly used in total hip arthroplasty (THA). This will be the first randomized, double-blind, prospective study to compare lidocaine to bupivacaine spinal anesthesia in THA patients. The objective of this study is to compare the two spinal anesthesia treatments with the primary outcome of transient neurological symptoms (TNS). The study will be conducted on healthy adult volunteers who are indicated for THA and agree to have spinal anesthesia. All patients will be randomized by a computer program and will receive either lidocaine or bupivacaine spinal anesthesia prior to their THA. Prospectively collected data will be obtained from the patient charts. In addition to TNS, other outcomes include urinary retention, hypotension, ambulation and length of hospital stay. We predict there will be no difference between lidocaine and bupivacaine spinal anesthesia in THA patients with respect to TNS and other outcome measures.

INTRODUCTION/BACKGROUND

A. Specific Aims

Most surgeons would agree total hip arthroplasty (THA) is one of the most successful surgical interventions. However, when it comes to the type of anesthesia to improve THA outcomes, surgeons do not agree. General anesthesia has been shown to be associated with increases in adverse events, increased operating room times and increased length of stay [Basques, Helwani]. Therefore, more surgeons are turning to spinal anesthesia for better pain control, decreased need for narcotics resulting in less nausea, sooner recovery of bowel function, and faster participation in physical therapy. All of these factors can lead to a sooner discharge from the hospital, which would lead to significant cost savings.

Transient neurological symptoms (TNS) are a concern of using spinal anesthesia and have been shown to occur up to 16-40% of the time with lidocaine [Ligouri, Capelleri, Hodgson, Keld]. There is no known cause of TNS. Symptoms have been described as pain, dysesthesia, or both that occur in the legs or buttocks and urinary retention after recovery from spinal anesthesia. Intensity of pain varies but can be quite severe. Symptoms can appear in a few hours, for up to 24 hours after surgery [Pollock].

The risk of developing TNS after spinal anesthesia with lidocaine has been shown to be higher when compared to other anesthetics [Zaric]. Lidocaine is the most widely used anesthetic due to its rapid onset, intense nerve blockade, and short duration of action. The use of spinal anesthesia with lidocaine has been shown in knee arthroscopy, general surgery, and obstetric literature [Valanne, Cappelleri, Ben-David B, Casati, Philip].

However, it is unknown whether there are differences between patients who undergo spinal anesthesia with lidocaine versus bupivacaine in THA. This knowledge is important because it has been shown that bupivacaine spinal anesthesia is more effective than lidocaine with minimal adverse effects [Gozdemir]. A large randomized, prospective study is needed to prove the difference between the two types of anesthesia.

The primary goal of this study is to evaluate the incidence of TNS between lidocaine and bupivacaine spinal anesthesia in THA patients. This will be done through examination of the patient records prospectively and telephone questionnaire after randomization to lidocaine or bupivacaine spinal anesthesia in THA patients.

Specific Aim 1: To determine the incidence of TNS after spinal anesthesia with lidocaine versus bupivacaine in THA patients.

Hypothesis: There will be no difference in TNS after surgery between lidocaine and bupivacaine spinal anesthesia in THA patients.

Specific Aim 2: To compare urinary retention after spinal anesthesia with lidocaine versus bupivacaine in THA patients.

Hypothesis: There will be no difference in urinary retention after surgery between lidocaine and bupivacaine spinal anesthesia in THA patients.

Specific Aim 3: To compare timing of ambulation after spinal anesthesia with lidocaine versus bupivacaine in THA patients.

Hypothesis: There will be no difference in timing of ambulation after surgery between lidocaine and bupivacaine spinal anesthesia in THA patients.

Specific Aim 4: To compare incidence of hypotension after spinal anesthesia with lidocaine versus bupivacaine in THA patients.

Hypothesis: There will be no difference in incidence of hypotension between lidocaine and bupivacaine spinal anesthesia in THA patients.

Specific Aim 5: To compare length of hospital stay after spinal anesthesia with lidocaine versus bupivacaine in THA patients.

Hypothesis: There will be no difference in length of hospital stay between lidocaine and bupivacaine spinal anesthesia in THA patients.

RESEARCH DESIGN

This is a single-center, prospective, randomized, double-blind study to evaluate the effectiveness of spinal anesthesia with lidocaine versus bupivacaine in subjects undergoing total hip arthroplasty. A total of 93 subjects per group will be enrolled in this study. All subjects will be blinded to treatment. Subjects screened at the [REDACTED] [REDACTED] c who meet the inclusion criteria, will be offered participation on the study.

Adult patients, age 18-90 years old who satisfy the inclusion criteria and do not meet the exclusion criteria will be enrolled. The enrollment period for this study is one year. Demographics obtained will be age, sex, height, weight, laterality and body-mass index (BMI).

Randomization: Patients will be randomized in a blocked fashion to receive either lidocaine or bupivacaine. Randomization will occur after informed consent has been obtained from the patients and after the surgeon has completed the preoperative screening examination. To minimize potential patient bias, each patient will be counseled that both anesthesia techniques are used in standard clinical practice. Patients will be blinded to their randomization until all study visits have been completed. The randomization module in REDCap, a secure, web based application for building and managing online surveys and databases, will be used to randomize the patients. A 1:1 block randomization model will be created by the clinical research coordinator. Each block will contain a random sequence of numbers in groups of twenty (i.e. 1 = lidocaine, 2 = bupivacaine). This sequence will be used to allocate patients to treatment groups. The investigators will be blinded to the allocation sequence.

SOURCE OF RESEARCH MATERIAL

Source of Research Material	Standard of Care? (Y/N)
Demographics [i. e., age, sex, height, weight, laterality and body-mass index (BMI)]	Y
Case Report Form (CRF)	N
History and physical exam	Y
Spinal Anesthesia Medication	Y
Preoperative Time	Y
Intraoperative Time	Y
Postoperative Time	Y
Time of PACU discharge	Y
Time of ambulation	Y
Vital Signs	Y
Urinary retention (intermittent catheter or foley catheterization)	Y
Date of admission	Y
Date of discharge	Y
TNS	Y

The following data for the study will be obtained from the subject's inpatient medical chart:

- Demographics [i. e., age, sex, height, weight and body-mass index (BMI)].
- TNS: during hospital stay and questionnaire after discharge
- Urinary retention: use of intermittent catheter or foley catheter
- Hypotension: defined as systolic blood pressure <90mmHg
- Operating Room Times: preoperative, intraoperative, postoperative
- Length of Stay: calendar days in the hospital
- Ambulation: Timing of ambulation during hospital stay

All data will be entered on a case report form (CRF), which will not have any identifiable patient information on it, only the patient's study number and initials will appear.

Inclusion and Exclusion Criteria

Inclusion criteria: Subjects meeting all of the following may continue in the study:

- Subject must be at least 18 years of age and no older than 90 years of age; of either sex
- Radiographic evidence of symptomatic osteoarthritis in one or bilateral hips. Osteoarthritis will be defined as pain with weight-bearing at the hip articulation together with radiographic findings as described below.
- Indicated for total hip arthroplasty
- Agreement to undergo spinal anesthesia for surgery

Exclusion criteria: Subjects meeting any of the following will be withdrawn from the study

- Patient refusal to undergo spinal anesthesia
- Patients with a known history of lumbar or sacral spinal fusion.
- Patients with a known history of prostate, urological, or kidney surgery.
- Patients who need monitoring of urine output during surgery (including patients with confirmed renal disease, renal failure, chronic renal insufficiency, or an indwelling catheter at the time of surgery).
- Current infection at site of injection
- Women of child-bearing potential who are on Medicare (child-bearing potential will be determined prior to surgery per Anesthesia standard of care)
- Hypovolemia
- Indeterminate neurologic disease
- Allergy or hypersensitivity to the study medications
- Currently taking any anti-coagulation medications or coagulopathic
- Increased intracranial pressure
- Subject is unable to make his/her own decision regarding the informed consent
- Subject is unable to read/understand English

Subject Screening Procedures. History and physical examination, hip radiographs, indication for total hip arthroplasty.

Description of the Recruitment and Consent Process

Potential study participants will be identified in the Emory Orthopaedic and Spine Center outpatient clinic by the study team (Principal Investigator (PI), Co-Investigator (Co-I), or research coordinator). The patient's history and physical examinations and hip radiographs will be evaluated to determine if the inclusion/exclusion criteria are met. Subjects will have the study procedures, risks and benefits explained to them by a study team member (PI, Co-I, and/or research coordinator). The patient will be given the opportunity to read the informed consent and given time to ask questions prior to consenting for the study. Once the subject has read the consent form and had time to ask questions, they should be asked to explain their understanding of the requirements of the study. Subjects should be asked to voluntarily sign the consent form. The subject must be able to self-consent to be eligible. The following procedures will be conducted and documented for all subjects:

- Informed Consent/HIPAA Authorization form (ICF/HIPAA form)
- Evaluation of compliance with inclusion and exclusion criteria
- Known Medication allergies

Subjects who sign the ICF/HIPAA Form and who agree to the study procedures may be enrolled in the study. Following subject enrollment, if it is determined by the investigators that he/she does not meet inclusion/exclusion criteria, or a medical situation arises that causes the subject to be unable to continue in the study, the patient will be

withdrawn from the study and considered enrolled, but “withdrawn by primary investigator.” Subjects may choose to withdraw at any time.

There is no plan to compensate enrolled subjects for their participation in the study.

Drugs, Dietary Supplements, Biologics, or Devices.

Patients in the intervention arms will receive one dose of either lidocaine or bupivacaine spinal, per Anesthesia standard of care for spinal anesthesia. The equipment is included in a tray that includes a 24 gauge pencil point spinal needle with introducer, and 22 gauge Quincke needle that are both 3.5 inches long. The approach will be either midline or paramedian with the patient sitting or lateral per Anesthesiologist preference and based on the patient.

Medications:

1. Bupivacaine: 0.75% hyperbaric in dextrose. Dose is primarily dependent on patient height 7.5-9mg </= 5 feet tall to 15mg >/= 6 feet tall.
2. Lidocaine: 2% isobaric. Dose is primarily height dependent 40mg for </= to 5 feet tall to 100mg >/= 6 feet tall.
3. Any additive medications to assist with pain control will be at the discretion of the Anesthesiologist and will be recorded for comparison. Additive medication will be per standard anesthesia protocol

The administration of either treatment will occur in a double-blinded fashion. Neither the patient receiving the medication nor the surgeon or investigators collecting study outcome data will be aware of whether or not the patient received lidocaine or bupivacaine. Due to patient safety concerns, the Anesthesiologist will not be blinded. Both treatment groups will receive a standard postoperative total hip arthroplasty pathway.

Study Procedures/Research Interventions

Potential study subjects will be identified in the Emory Orthopaedics and Spine Center clinic by history and physical and hip radiographs. A protocol approved investigator or research coordinator will approach the potential subject and briefly explain the study. Following the subject’s agreement to participate in the study and attainment of proper consent, the subject’s baseline Case Report Form (CRF) will be completed. The Inclusion/Exclusion Criteria outlined in this protocol should be reviewed for determination of subject eligibility and continuance in the study. For female subjects, a negative pregnancy test will be obtained to continue in the study. Only when eligibility has been determined, will the subject be allowed to participate in the planned study procedures. Final eligibility will be determined by the PI or Co-I.

Assessment	Study Day/Period							
	Screening	Op Day	POD #1	POD #2	POD #3	POD #4	1 week post-op	2 week post-op
History/Physical Exam	x							
Hip Radiographs	x							
Pregnancy test (females-if needed)	x							
Informed Consent Discussion	x							
Demographics [i. e., age, sex, height, weight, laterality and body-mass index (BMI)]		x						
Randomization		x						
Study drug		x						
Admission Date		x						
Preop Time		x						
Intraop Time		x						
Postop Time		x						
Vitals		x	x	x	x	x		
Ambulation		x	x	x	x	x		
Anesthesia Duration								
Urinary retention		x	x	x	x	x		
TNS: weakness, numbness, parasthesias, etc.		x	x	x	x	x	x	x
Discharge date		x	x	x	x	x		

TNS Evaluation

The duration of the anesthesia, defined as the time until the subject had normal sensation and was able to lift both extremities, will be recorded. The subject will be contacted on the first and third postoperative days by the study team, who are blinded to the anesthetic used and only informed of the subjects' data and telephone number. Following a prepared questionnaire [APPENDIX B], the study team member will ask about symptoms of TNS and pain not associated with the operation area. The subject will be asked to specify the location of the symptoms and grade the complaints after a verbal analogue scale from 0 to 10, with zero as no discomfort and ten as unbearable discomfort. The subject will be asked about the time to full mobilization and time of first voiding.

Another follow-up call will be made within 7 and 14 days post-operatively. If any subject continues to have symptoms, further follow-up evaluation will proceed on a case-by-case basis until the problem resolved, the subject is unable or unwilling to be contacted again, or the primary physician requests no further follow-up calls by the study team. The remaining data points will be prospectively obtained from the inpatient chart and recorded on the CRF.

Data Collection

A subject key listing name, medical record number (MRN), age, sex, study number and treatment received will be kept in electronic format, as well as in the research binder stored in a secure locked file cabinet.

Radiographs will be obtained at the initial clinic visit per standard of care. Demographic data, including height, weight, BMI, sex, laterality and age, at the initial clinic visit will be recorded on the CRF. During the subject's inpatient hospitalization, study treatment, vital signs, TNS, ambulation, urinary retention and length of stay will be recorded on the CRF. All data collected on the CRF will be kept in REDCap as well as in the research binder. The CRF will not have any identifiable subject information, only the study number and subject's initials.

Data from the paper CRFs will be entered into an electronic database in REDCap by a study team member. The database will be made available to all investigators electronically. Data analysis will be performed by the investigators which will also be performed on a password enabled computer. There will be no patient identifiers in the data provided to the investigators, only the subject number.

Primary (i.e., primary outcome variables) and secondary endpoints

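### A single published block size of twenty lets anyone who sees past treatments predict some assignments: a modest concealment weakness, firmest for the research coordinator

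*Combined protocol and SAP*

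**What the plan says.** - **Allocation.** Research Design opens: "This is a single-center, prospective, randomized, double-blind study". Its Randomization paragraph adds "A 1:1 block randomization model will be created by the clinical research coordinator" and "Each block will contain a random sequence of numbers in groups of twenty". No other block size and no strata are given.
- **Concealment.** The statement on hiding the list is "The investigators will be blinded to the allocation sequence". Nothing is said about keeping the block size from recruiters.
- **Timing.** Randomization follows consent and the surgeon's screening examination. The assessment schedule places it on the day of surgery.
- **Recruitment and eligibility.** Under Description of the Recruitment and Consent Process, patients are identified "by the study team (Principal Investigator (PI), Co-Investigator (Co-I), or research coordinator". Under Study Procedures, the PI or Co-I decides final eligibility.
- **Sight of treatments given.** Data Collection describes a subject key that includes treatment received. It also says "study treatment, vital signs, TNS, ambulation, urinary retention and length of stay will be recorded on the CRF", that CRF data are kept in REDCap, and "The database will be made available to all investigators electronically". Risks/Benefits Assessment gives the key to the coordinator alone and, through a garbled double negative, appears to deny it to investigators. Data and Safety Monitoring gives the PI and study team access to a master list, and has the PI review and sign every CRF. The Medications text says the surgeon and the investigators collecting outcomes will not know the drug, and adds "Due to patient safety concerns, the Anesthesiologist will not be blinded".

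**The concern.** In a 1:1 block of known length, the remaining assignments are fixed once one drug has been used ten times, and before that the drug used less often is the better guess. Blinding people to the future list does not remove this if they can count the past.

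The stake is selection before randomization. The protocol's own background gives a higher TNS risk with lidocaine (16-40%, against under 5% with bupivacaine). Someone expecting lidocaine next could therefore have a reason to reschedule a particular patient or judge that patient ineligible. TNS is reported by the patient, and an intention-to-treat analysis cannot repair an imbalance created before assignment. The issue is separate from who builds the list: it would remain if an independent person built it and past treatments stayed visible.

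**Working it through.** **Inputs.** Block length 20, ten per arm, one center, no strata (Research Design). 93 per group, so 186 in total (Sample size and power considerations). Exact binomial power of the two-sided pooled Z test for 0.20 against 0.05 is 0.8973 at 92 per group and 0.9006 at 93, so the plan's 93 is reproduced and is not in question. 186 = 9 × 20 + 6: nine full blocks and six patients of a tenth.

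**Certain assignments, all past assignments seen, no lag.** The chance that the last k assignments of a block all go to one arm is P(k) = 2·C(20−k,10)/C(20,10):

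- P(1) = 1, P(2) = 0.474, P(3) = 0.211, P(4) = 0.087.
- So the 20th assignment is always certain, the 19th in 47% of blocks, the 18th in 21%, the 17th in 9%.
- Sum over k = 2m/(m+1) with m = 10, which is 20/11 = 1.82 per block.
- Nine blocks: 9 × 1.818 = 16.4 of 186 (8.8%). Nothing in the six-patient tenth block can be certain.

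**Correct guesses, always choosing the drug used less often.** Per full block: m + ½(4^m/C(2m,m) − 1) = 10 + ½(1,048,576/184,756 − 1) = 12.34 of 20, or 61.7%. The six-patient remainder adds 3.19. Total: 9 × 12.338 + 3.19 = 114.2 of 186, or 61.4%, against 50% by chance.

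**Effect of lag.** If L assignments fall unseen between the last one known and the one predicted, certainty needs the last L+1 or more of the block to be in one arm. The expected count is then 9 × the sum of P(k) for k ≥ L+1:

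- L = 1: 9 × (1.818 − 1) = 7.4.
- L = 3: 9 × (1.818 − 1 − 0.474 − 0.211) = 1.2, with 56.6% of guesses correct.
- L = 5: 0.1, with 55.0% correct.

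The planned pace is 186/52 = 3.6 patients a week. The documents give no interval between clinic and surgery. If it were about a week (an assumption), L would be between 3 and 4 for someone predicting from clinic.

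**Alternatives over 186 patients, no lag.**

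| Scheme | Correct guesses | Certain |
|---|---|---|
| Fixed 20 (plan) | 61.4% | 16.4 |
| One permuted 93:93 list | 54.3% | 2 × 93/94 = 1.98 |
| Random 16/20/24/28, undisclosed | 60.9% | block ends not known |
| Random 4/6/8, undisclosed | 68.0% | block ends not known |

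**Balance at the PI review after 60 participants.** Blocks of twenty are exactly balanced there (3 × 20). Under one list of 186, the hypergeometric chance of an imbalance of 8 or more is 27%.

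**The case against.** Four objections have force.

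- **Visibility to the PI and Co-I is not established.** The Medications text and one sentence of Risks/Benefits Assessment point against it. Database access is mentioned next to data analysis and may mean access at the end. Paper CRFs are entered only within a reasonable time, so REDCap may lag. The contents of the master list are not stated. This stands: for them the concern is conditional. It does not clear the coordinator, who recruits and holds the treatment key on any reading.
- **The Anesthesiologist.** A reader might infer that this unblinded clinician can steer patients. The documents do not describe the Anesthesiologist as recruiting, and do not say that one person sees every case in order, which counting requires.
- **Timing.** Because assignment happens on the day of surgery, someone in clinic would have to predict a later slot. This stands and removes most of the certainty. What remains is surgical scheduling, the final eligibility decision, and withdrawal by the investigator after enrolment.
- **Twenty is already a large block.** Also true: a fixed block of four would make 33% of assignments certain, against 9.1% in a full block here.

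A reader might also see harm in the fact that blocks of twenty give exactly 93 per arm with probability only 0.37 (C(10,3)²/C(20,6)). The worst split is 96:90, which moves the standard error of the difference from 0.0472 to 0.0477. That is immaterial.

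**Conclusion.** The concern holds as a modest concealment weakness. One disclosed block size makes up to about 16 of 186 assignments (8.8%) certain and 61.4% guessable, for someone who sees every past assignment in order with no delay. With one unseen intervening assignment about 7 are certain, and with three about 1. The firm case is the coordinator. For the PI and Co-I it depends on which access statements apply.

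A reader might go further and put a bias on the TNS comparison. For example, a 10-point difference in TNS risk between patients steered one way and the other would give 10 × (0.617 − 0.383) = 2.3 points. The documents do not support that figure. It needs no lag, action on every guess, and a baseline predictor of TNS that recruiters can see. The introduction says the cause of TNS is unknown, no predictor is given, and the exclusions already remove lumbar or sacral fusion and indeterminate neurologic disease. No bias estimate can be derived.

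**What to change.** 1. In the Randomization paragraph, replace the blocks of twenty with one computer-generated 1:1 permuted list of 186 (93 per arm), loaded into the same REDCap module. If blocking over time is wanted, use large, randomly varying sizes kept out of the protocol. This removes known block ends but leaves correct guesses near 61%. Avoid small random blocks, which raise them to 68%.
2. Have the list built and held by someone who neither recruits nor decides eligibility, and keep any block sizes with that person. A coordinator who both recruits and builds the list defeats any blocking scheme.
3. Reconcile the Medications text, Data Collection, Data and Safety Monitoring, and Risks/Benefits Assessment, so that treatment received is hidden from recruiters and from those deciding eligibility until enrolment is complete.

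Cost: one changed sentence, a new allocation table, an access rule, and reassigning the list (and sight of the treatment key) away from the coordinator. No extra patients are needed and the analysis is unchanged. The downside of the single list is slightly looser balance over time, including the 27% chance of an imbalance of 8 or more at the 60-participant review. That is minor in a one-year, single-center trial with no planned interim analysis.
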